6. TREATMENT

6.1 Treatment Administration

6.1.1. Sunitinib

Sunitinib will be provided by the Trial Sponsor. Sunitinib will be administered at a dose of 37.5 mg per day (1 capsule of 25 mg and 1 capsule of 12.5 mg) orally for 28 days on an ongoing basis. It must always be taken at the same time every day (or as close as possible) and capsules must be swallowed whole. Food does not appear to affect the bioavailability of the drug. A 37.5 mg dose was chosen based on the approved dose of sunitinib for the treatment of pancreatic neuroendocrine tumours (pNET). If the patient requires a sunitinib dose reduction, the dose adjustment stated in section 6.3 will be followed.

On days when TH-302 is also administered, sunitinib must be taken 2 hours before, or at least 2 hours after TH-302 infusion. Given its hypoxia-inducing ability in highly vascular tumour tissue and its TH-302-enhancing effect, sunitinib will be administered as monotherapy in the first week of treatment.

If, for any reason, the patient skips a dose or vomits after ingestion, a double dose should not be taken the following day. Treatment will resume on the following day with the usual daily dose. In contrast, if for any reason an additional dose is taken, the following day's dose should be skipped.

The study drug will be supplied in 25 mg and 12.5 mg capsules. The study drug must be handled and stored safely and as specified on the label. The label on the bottles will indicate the study protocol number, the medication or bottle number, the contents, instructions for use, storage instructions, the clinical trial declaration and the name of the sponsor. The patient number will be allocated to a bottle upon hand over.

Patients will be instructed as to its correct administration and that it must be kept at room temperature (15-25 °C) and out of the reach of children. Site staff must ensure that the patient understands the instructions for correct outpatient use of the drug.

Patients will receive enough medication until the next visit, and must return the containers with any surplus medication for it to be accounted for. This will take place on day 1 of each cycle prior to dispensation of medication for the next cycle. Any surplus medication returned by the patient for it to be accounted for will not be dispensed again, and the number of surplus sunitinib tablets will be recorded. If the dose is modified during a medical visit, the patient will return all surplus prior medication.

The patient will be questioned about treatment compliance at each study visit. For a patient to be deemed to adequately comply with the study treatment, at least 80% of the prescribed doses must be administered. The recording of these activities will comply with current regulations and guidelines.

6.1.2 TH-302

TH-302 will be provided by the Sponsor. The TH-302 dose administered will be 340 mg/m² by intravenous infusion over 30-60 minutes, on days 8 and 22 of each cycle. The dose should be adjusted according to body surface area. In the event of patient weight variation > 10%, the body surface area will be recalculated and the TH-302 dose readjusted. If the patient requires a TH-302 dose reduction, the dose adjustment stated in section 6.3 will be followed.

The TH-302 medicinal product is supplied in a 10 ml glass bottle and must be diluted prior to administration with a 5% commercial glucose solution (containing 278 mmol/L dextrose) for injection to a total volume of 500 ml (1000 ml for a total dose ≥ 1000 mg) per infusion to obtain the final desired concentration. The 5% glucose solution will not be provided.

Each dose of TH-302 will be prepared in an infusion bag without di-(2-ethylhexyl) phthalate (DEHP) with 5% glucose solution for clinical use and administered intravenously using an infusion pump and DEHP-free IV delivery system.

TH-302 should be administered under free-flow intravenous fluid, preferably through a central venous catheter, especially in the presence of extravasation risk factors. Administration through the small vessels in the hands or feet is not recommended.

Detailed instructions on dilution and administration are included in the pharmacy files. Preventive treatment will be added prophylactically for nausea or vomiting, following a regimen for moderately emetogenic chemotherapy.

Cases of perivascular erythema and hyperpigmentation at the infusion site have been reported. Severe cellulitis and tissue necrosis may manifest due to TH-302 extravasation during its administration. The necessary recommended and preventive measures should be taken for the administration of cytostatic drugs, thereby preventing complications during infusion. If any signs or symptoms of extravasation appear, the TH-302 infusion should be stopped and continued in another vein. The patient should be monitored closely to assess the evolution of the skin lesion given the progressive nature of extravasation lesions, and a plastic surgeon should be consulted if necessary.

Infusion reactions have also been observed during the administration of TH-302 characterised by swelling of the lips and urticaria, which respond to treatment with steroids and antihistamines. Include a steroid (such as dexamethasone or equivalent) in the pre-infusion antiemetic regimen is recommended. Signs and symptoms of hypersensitivity include fever, myalgia, headache, rash, pruritus, urticaria, angioedema, chest discomfort, dyspnoea, cough, cyanosis and hypotension. If the nature and severity of the reaction require the infusion to be discontinued, it should be determined whether it is an IgE-mediated process. If symptoms such as obstruction of the upper airways or hypotension are presented that suggest anaphylaxis or an anaphylactoid reaction, the investigator will assess whether to administer an antihistamine (such as slow intravenous or intramuscular diphenhydramine 25-50 mg orally, or equivalent) and a low-dose steroid (such as intravenous hydrocortisone 100 mg or equivalent). If the event is clearly anaphylactic, the administration of epinephrine (1/1000, 0.3-0.5 ml subcutaneously, or equivalent) should be considered, in addition to the standard treatments. In the case of bronchospasm, the administration of inhaled β-agonists will be assessed.

Depending on intensity, idiosyncratic reactions may also be treated with an antihistamine and steroids at low doses. Post-infusion reactions of the study drug will be assessed and treated in a similar way. Whenever a study drug infusion reaction occurs, the investigator should consult the medical monitor to determine the most suitable procedure for future infusions.

TH-302 must be handled and stored safely and as specified on the label and in the Investigator's Brochure. The label on the bottles will indicate the study protocol number, the medication or bottle number, the contents, instructions for use, storage instructions, the clinical trial declaration and the name of the sponsor. The patient number will be allocated to a bottle upon hand over.

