6.3.6. Concomitant treatment

All concomitant medication, including any drug administered within 4 weeks (28 days) prior to the day 1 visit and 30 days after the last dose of the study drug, must be recorded in the case report form, together with the reason for administration.

The patient should be informed about the importance of consulting the investigator prior to taking additional medications.

Concomitant medication includes any vitamins, herbal remedies, over-the-counter drugs and prescribed medicines.

Any additional treatment that becomes necessary during the study, and any change to concomitant drugs, must be recorded in the corresponding section of the case report form, including the name, dose, duration and indication of each drug.

Should medication be administered intermittently, or in relation to an adverse event, this adverse event should be recorded on the adverse event form of the case report form.

- **Disallowed concomitant treatment:**
 - Other oncology drugs (chemotherapy, immunotherapy, targeted therapy) during the treatment phase, whether approved healthcare drugs or under clinical trial.
 - Drugs that are known to cause QT interval prolongation, given the risk of developing polymorphic ventricular tachycardia. (Annex 4)
 - Strong or moderate CYP3A4 inhibitors

If, during the study, a patient requires treatment with one of these drugs for a limited period of time, TH-302 and sunitinib will not be administered simultaneously. Treatment will be reviewed together with the medical monitor, who will supply the dosage rules based on the half-life of the medicinal products, TH-302 and sunitinib, in addition to other clinical considerations. The medical monitor will advise the investigator, who will assess the search for alternative medicines.

- **Concomitant treatment not recommended:**

- Chronic immunosuppressant treatment, including systemic corticosteroids. Short courses of topical/inhaled or systemic corticosteroids are permitted
- Herbal products

For up-to-date information on drug interactions (substrates, inhibitors or inducers), visit the following website:

<http://www.fda.gov/Drugs/DevelopmentApprovalProcess/DevelopmentResources/DrugInteractionsLabeling/ucm093664.htm#classSub>

- **Permitted concomitant treatment**

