ANNEX 4. NON-PERMITTED CONCOMITANT MEDICATION

I. Drugs that cause QT interval prolongation, with the risk of developing polymorphic ventricular tachycardia

Amiodarone	Domperidone	Pentamidine
Arsenic trioxide	Droperidol	Pimozide
Astemizole	Erythromycin	Probucol
Azithromycin	Flecainide	Procainamide
Chloroquine	Halofantrine	Quinidine
Chlorpromazine	Haloperidol	Sotalol
Cisapride	Ibutilide	Sparfloxacin
Citalopram	Levomethadyl	Terfenadine
Clarithromycin	Mesoridazine	Thioridazine
Disopyramide	Methadone	Vandetanib
Dofetilide	Moxifloxacin	

II. Strong or moderate CYP3A4 inducers

CYP3A4 enzyme-inducing drugs

Bosentan	Glutethimide	Rifabutin*
Carbamazepine*	St John's Wort*	Rifampicin*
Dexamethasone	Modafinil	Rifapentine*
Efavirenz	Nafcillin	Sulfadimidine
Felbamate*	Nevirapine*	Sulfinpyrazone
Phenobarbital*	Omeprazole	Troglitazone
Phenytoin*	Primidone*	Troleandomycin

*Strong CYP3A4 enzyme inducers

CYP3A4 enzyme-inhibiting drugs

Amprenavir*	Fosamprenavir*	Grapefruit or any product containing grapefruit*
Atazanavir*	Gestodene	Posaconazole*
Boceprevir*	Indinavir*	Ritonavir*
Clarithromycin*	Itraconazole*	Saquinavir*
Clotrimazole	Ketoconazole*	Telaprevir*
Conivaptan*	Lopinavir*	Telithromycin*
Delavirdine*	Mibefradil* (withdrawn USA)	Troleandomycin
Diltiazem	Miconazole*	Verapamil*
Erythromycin*	Nefazodone*	Voriconazole*
Ethinylestradiol	Nelfinavir*	Grape or any product containing grape*
Fluoxetine	Nicardipine	

* Strong CYP3A4 enzyme inhibitors.

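### The only steroid that section 6.1.2 names for TH-302 premedication is on the Annex 4 non-permitted list, and section 6.3.6 does not resolve the conflict

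*Protocol*

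**What the plan says.** Four places in the protocol bear on this point.

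- **Section 6.1.2 (TH-302).** Antiemetic cover accompanies TH-302: "Preventive treatment will be added prophylactically for nausea or vomiting, following a regimen for moderately emetogenic chemotherapy". The same section then describes infusion reactions and adds: "Include a steroid (such as dexamethasone or equivalent) in the pre-infusion antiemetic regimen is recommended". Hydrocortisone also appears in this section, but only for treating a reaction that has already occurred.
- **Annex 4.** Its title is "ANNEX 4. NON-PERMITTED CONCOMITANT MEDICATION". Part II is headed "II. Strong or moderate CYP3A4 inducers", and the table of inducing drugs beneath it contains the entry "Dexamethasone". An asterisk in that table marks "Strong CYP3A4 enzyme inducers"; dexamethasone has no asterisk. A table of inhibitors follows under the same part II heading.
- **Section 6.3.6 (Concomitant treatment).** The disallowed list has three items: other oncology drugs, QT-prolonging drugs, and "Strong or moderate CYP3A4 inhibitors". Inducers are not named. The reference to the annex is attached to the QT item alone: "Drugs that are known to cause QT interval prolongation, given the risk of developing polymorphic ventricular tachycardia. (Annex 4)". If a patient needs a drug from this list for a limited time, the section restricts simultaneous administration of TH-302 and sunitinib and refers the case to the medical monitor. Elsewhere the section advises against chronic immunosuppression, including systemic corticosteroids, but allows brief courses.
- **Section 7.2, exclusion criterion 6.** This covers strong CYP3A4 inhibitors or inducers in the 7 days before enrolment.

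**The concern.** The drug offered as the example in one section is listed as non-permitted in another, with no exception in either. Two sites reading the protocol in good faith could therefore act differently.

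The question recurs with treatment. TH-302 is given on days 8 and 22 of each 28-day cycle, so any site using the named example meets it twice per cycle for as long as TH-302 continues. The protocol plans 10 sites and a single arm. A difference in premedication, or in whether study drug is given on an infusion day, would be a difference in how the one regimen under test is delivered.

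The steroid advice is tied to infusion reactions. A site that avoids dexamethasone because of Annex 4 is told only that an equivalent will do; no other agent is named for pre-infusion use.

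**Working it through.** The check is a comparison of texts. The plan gives no figure on this point and no calculation applies.

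**Step 1. Which CYP3A4 drugs are restricted, and when?**

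| Place | Period | Inhibitors | Inducers |
|---|---|---|---|
| Section 7.2, criterion 6 | 7 days before enrolment | strong | strong |
| Section 6.3.6 | during treatment | strong or moderate | not named |
| Annex 4, part II | non-permitted list | table present, not named in the heading | strong or moderate, named in the heading |

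The three scopes differ. Section 6.3.6 names inhibitors only, while the annex heading names inducers only, although both kinds of drug are tabulated beneath it. Criterion 6 shows that the protocol regards induction as relevant at least before enrolment, so the annex table cannot simply be dismissed as stray text.

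**Step 2. Where does dexamethasone fall?**

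- Criterion 6 does not reach it: it is not marked as a strong inducer, and the criterion ends at enrolment.
- The disallowed list in section 6.3.6 does not reach it: inducers are absent, and the annex is cited only for QT-prolonging drugs.
- Annex 4, part II does reach it: it is listed by name, under a heading that includes moderate inducers.
- Section 6.1.2 recommends it as an example.

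The prohibition therefore rests on the annex alone, and it meets a recommendation in the body text.

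**Step 3. Does the short-course allowance settle it?**

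Not clearly. That allowance qualifies the advice on chronic immunosuppression; it is not an exception to the CYP3A4 rule. Nor does the section say whether a dose repeated at every infusion over an open-ended treatment period is a short course. A single dose on days 8 and 22 could reasonably be read as one, but the text leaves this to the reader.

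**Step 4. What can a site do?**

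| Reading | Action at infusion | Section 6.1.2 | Annex 4 |
|---|---|---|---|
| Equivalent steroid not in Annex 4 | TH-302 given | met | met |
| Dexamethasone, as in the example | TH-302 given | met | departed from |
| Annex 4 part II read into section 6.3.6, dexamethasone judged necessary | study drug may be withheld pending medical monitor advice | premedication followed, infusion in doubt | the listed drug is treated as disallowed |

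On the third reading the effect could extend to dosing. Section 6.3 has a postponed day 8 or day 22 dose skipped, so a site applying that rule here would lose the dose.

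**The case against.** The strongest case on the other side is that the operative section does not prohibit dexamethasone. Section 6.3.6 lists what is disallowed, and inducers are not on the list. It deals with steroids directly and allows brief systemic use. The rule on simultaneous administration refers back to the section's own list, so it reaches dexamethasone only if part II of the annex is imported into a sentence that does not cite it. It would also be odd to read section 6.1.2 as recommending a premedication that bars the infusion it precedes. All of this stands, and it makes the third reading in the working the least natural. It does not remove the annex entry, which carries a non-permitted title and names the drug.

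Three stronger readings are tempting, and the documents do not support them.

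- **A reader might infer that sites cannot comply with both texts.** They can. The advice is a recommendation, dexamethasone is an example, and an equivalent is expressly allowed. Hydrocortisone, named in the same section for another purpose, is not in the Annex 4 tables, so unlisted steroids exist within the protocol's own vocabulary. This is an observation about the lists, not a suggestion of what to give.
- **A reader might infer that sunitinib exposure is affected.** The protocol links CYP3A4 to sunitinib metabolism and genotypes CYP3A4 variants, but no figure in either document shows that intermittent dexamethasone changes exposure, and the annex does not mark it as a strong inducer.
- **A reader might infer that the analysis is affected through protocol deviations.** The SAP defines one analysis set, by eligibility (section 1.5.1.1). It has no per-protocol set, and its listed safety outputs (section 1.5.5.1) include no deviation analysis. The response-rate denominator does not depend on premedication.

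**Conclusion.** The contradiction is real but limited. The only steroid named for TH-302 premedication is on the protocol's own non-permitted list, and the section that should govern concomitant treatment neither confirms nor lifts that listing. A compliant route exists through an unlisted equivalent. The problem is therefore inconsistent instruction, with room for sites to differ, and not an impossible requirement.

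As to size, up to two infusions per 28-day cycle are open to the question in any patient whose site uses the named example. The documents give no basis for estimating how many sites would choose it, so all infusions in all patients is only an upper bound. The withholding of study drug depends on the further assumption that Annex 4 part II is read into section 6.3.6.

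The point deserves correction because these are conflicting stated rules on a drug that could be used repeatedly, and the correction is cheap. The texts must be reconciled; nothing here says which of them is right.

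**What to change.** The sponsor should reconcile section 6.1.2, section 6.3.6 and Annex 4 so that they state one rule on two questions:

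1. Are CYP3A4 inducers, inhibitors or both disallowed during treatment, and at what strength? The heading of Annex 4 part II and the list in section 6.3.6 should then agree, and section 6.3.6 should cite every part of the annex that it relies on.
2. Is pre-infusion dexamethasone excepted from the annex? The answer should appear in all three places and should say whether repeated pre-infusion doses fall under the short-course steroid allowance and whether the rule on simultaneous administration applies to them.

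Both answers are clinical choices for the sponsor, and none is proposed here. The cost is a correction to protocol text and annex, communicated to sites. It needs no change to sample size, endpoints or the SAP's analysis sets.

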6.2. Duration of Treatment

Treatment with TH-302 in combination with sunitinib will continue until disease progression, unacceptable toxicity, non-compliance with the protocol, the patient's withdrawal of informed consent or at the discretion of the investigator. **In case of withdrawal of the study medication for toxicity, the patient will continue follow-up according to the scheduled study activities, and the investigator following the patient shall be responsible for initiating another systemic treatment option if deemed appropriate.**

6.3. Titration of the Study Drug

All dose modifications must be conducted according to the most severe preceding toxicity, as classified by the *National Cancer Institute Common Terminology Criteria for Adverse Events* (NCI-CTCAE, version 4.0).

As far as possible, an attempt should be made to follow the dose and scheduled regimen. However, in case of an adverse event, administration of the study drug should be titrated as described below.

The patient should notify the investigator of the date of onset of any adverse signs and symptoms.

Dose modifications to both treatments may be required in 3 different situations:

- During a cycle: treatment is discontinued until recovery and the dose is reduced, if necessary, during a particular treatment cycle.
- Between different cycles: treatment administration is delayed in the next cycle due to persistence of residual toxicity at the beginning of a new cycle.
- During the following cycle: the dose is reduced in the following cycle, taking into account the toxicity exhibited in the previous cycle.

In the event of treatment delay, proceed as follows:

- On day 1 of a cycle, if the administration of sunitinib must be postponed, the whole cycle must be delayed.

A phase II trial to assess the activity and safety of TH-302 in combination with sunitinib in patients

- On days 8 or 22, if the administration of both drugs must be postponed, that dose must be skipped.
- On days 8 or 22, if the administration of just 1 drug must be postponed, that dose will be skipped and the cycle will not be delayed, but rather the other drug will be administered on its own.

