6.3.1. Discontinuation of Treatment

The treatment will be temporarily discontinued until the resolution of \leq grade 2 toxicity. Depending on the duration of treatment discontinuation, this will either lead to the loss of all subsequent scheduled doses within the same cycle, or even delay the start of the next cycle. If the patient recovers from the adverse event within the same cycle, therapy may be continued in that cycle. Any missed doses for toxicity will not be made up for within the same cycle.

Dose reduction when reintroducing the treatment is determined below (section 6.3.3), unless, in the event of disagreement, the investigator prefers to discuss it with GETNE [contact]. If a dose is reduced within a cycle, the patient should return to the site to receive the new treatment dose.

If treatment discontinuation lasts $>$ 4 weeks, for reasons other than study treatment toxicity (non-cancer surgery, etc.), GETNE must be consulted before reintroducing the study drug

Treatment will be discontinued permanently in the following situations:

- The patient requires more than 2 dose-reduction steps.
- The patient requires more than 4 weeks delay (one full cycle) to restart treatment due to study treatment toxicity.

In patients for whom recovery from treatment toxicity involves treatment suspension lasting more than 4 weeks, or delaying a treatment cycle, but there is a clear clinical benefit in the opinion of the investigator, reintroduction of the treatment may be discussed with GETNE

Patients who discontinue treatment with TH-302 may continue receiving sunitinib as monotherapy within the trial.

Under no circumstances may patients receive TH-302 as monotherapy. In the event that the administration of sunitinib must be discontinued, the administration of TH-302 will also be discontinued.

Patients who permanently discontinue TH-302 and sunitinib will abandon active treatment and enter the follow-up phase.

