6.3.4. Dose Titration According to the Type and Severity of Toxicity

Table 2. Titration according to haematological toxicity

ABSOLUTE NEUTROPHIL COUNT (ANC) (/μl)	AND /OR	PLATELET COUNT (/μl)	DOSE LEVEL WHEN REINTRODUCING TH-302		SUNITINIB
			Day 8	Day 22	
≥ 1500	AND	≥ 100,000	Starting	Starting	Starting
1000-1499	AND	75,000-99,999	Delay	Delay	Starting
500-999	OR	50,000-74,999	Delay and reduce one level in following cycles	Delay and reduce one level in following cycles	Reduce one level
< 500	OR	< 50,000	Delay and reduce one level in following cycles	Delay and reduce one level in following cycles	Reduce one level

A phase II trial to assess the activity and safety of TH-302 in combination with sunitinib in patients

Table 3. Titration according to non-haematological toxicity

TH-302			
Toxicity grade	Toxicity	Discontinuation	Dose after recovery
Grade 2	Except for asthenia, alopecia, nausea, vomiting and diarrhoea	Until \leq grade 1 recovery	Starting
	Unacceptable skin abnormality	Until \leq grade 1 recovery	Reduce one level (-1)
Grade 3	Except for nausea and vomiting	Until \leq grade 1 recovery	Reduce one level (-1)
Grade 4	Potentially fatal (drug-related)	Permanent discontinuation	N/A
	Others such as non-life threatening asthenia or pulmonary embolism	Until \leq grade 1 recovery	Reduce two levels (-2)

Table 4. Titration according to non-haematological toxicity

Sunitinib			
Toxicity grade	Toxicity	Discontinuation	Dose after recovery
Creatinine > x2 upper limit of normal (ULN)	Irrespective of the cause	Until creatinine \leq x2 upper limit of normal (ULN)	Reduce one level (-1)
Grade 2	Except for asthenia, alopecia, nausea, vomiting and diarrhoea	Until \leq grade 1 recovery	Starting
Grade 3	Except for nausea and vomiting	Until \leq grade 1 recovery	Reduce one level (-1)
Grade 4	Potentially fatal (drug-related)	Permanent discontinuation	N/A
	Others such as non-life threatening asthenia or pulmonary embolism	Until \leq grade 1 recovery	Reduce one level (-1)

Table 5. Titration according to ECG QTc interval prolongation

	Presence of a reversible cause	Unidentified reversible cause

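### When only sunitinib is held on day 8 or 22, section 6.3 read literally directs TH-302 alone, which section 6.3.1 prohibits; the two rules need reconciling

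*Protocol*

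**What the plan says.** Protocol section 6.3 lists what to do when treatment is delayed. The day 1 bullet names sunitinib and delays the whole cycle. The first bullet for days 8 and 22 covers a hold of both drugs and skips the dose. The second covers a hold of one drug, and its instruction is: "that dose will be skipped and the cycle will not be delayed, but rather the other drug will be administered on its own". It does not say which drug.

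Section 6.3.1 follows directly. It allows a patient who stops TH-302 to stay on sunitinib alone. For the reverse case it says: "Under no circumstances may patients receive TH-302 as monotherapy". It then adds: "In the event that the administration of sunitinib must be discontinued, the administration of TH-302 will also be discontinued".

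The SAP does not settle the matter. Its section 2.5 restates the planned regimen and has separate tables of reductions, delays and omissions for each drug (Tables 9 and 11).

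**The concern.** If the held drug is sunitinib, the other drug in the section 6.3 bullet is TH-302. One section then tells the site to infuse, and the next tells it not to. The patient concerned has just had one study drug held, so this is a question about an active dosing order and not only about drafting.

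There is also a consequence for interpretation. Section 6.1.1 bases the regimen on hypoxia induced by sunitinib enhancing TH-302. Infusions given while sunitinib is held would put a regimen that section 6.3.1 prohibits into the safety and response data of a single-arm study of the combination. The planned exposure tables would not identify those infusions, because omissions are counted drug by drug.

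**Working it through.** No formula produces this point, and the plan states no figure to reproduce. The check is a comparison of the rules, case by case.

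**Step 1: the three possible holds on day 8 or 22.**

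| Drug held | Section 6.3 | Section 6.3.1 | Result |
|---|---|---|---|
| Both | Skip the dose | Nothing contrary | Consistent |
| TH-302 only | Give sunitinib alone | Sunitinib alone is allowed | Consistent |
| Sunitinib only | Give TH-302 alone | TH-302 alone is barred | Contradiction |

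Only the third case conflicts. On day 1 the question does not arise, because no TH-302 is due.

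**Step 2: does the ban apply only to lasting discontinuation?** If it did, a single postponed dose would fall outside it. The protocol's usage does not support that limit. Section 6.3 describes a hold within a cycle as "During a cycle: treatment is discontinued until recovery and the dose is reduced, if necessary". Section 6.3.1 itself begins "The treatment will be temporarily discontinued until the resolution of" toxicity to a stated grade. Where section 6.3.1 means a permanent stop, it says so. The sentence that ties TH-302 to sunitinib carries no such qualifier, and the protocol does not define monotherapy.

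**Step 3: does any text rank the two rules?** Neither section refers to the other. Sections 6.3.2 to 6.3.4 and the SAP exposure section do not address TH-302 during a sunitinib-only hold.

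**Step 4: can the dose tables in section 6.3.4 produce a sunitinib-only hold?**

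- Table 2 (haematological) delays TH-302 in situations where sunitinib continues, never the reverse. Section 6.3.2 likewise sets a higher neutrophil threshold for restarting TH-302 (1,500) than for sunitinib (1,000).
- Tables 3 and 4 (non-haematological) have matching hold triggers at grades 2, 3 and 4. TH-302 has one extra row, for skin abnormality.
- Table 5 (QTc) tells the site, at grade 3, to discontinue treatment without separating the drugs.
- Table 4 has one row without a named counterpart in Table 3: creatinine above twice the upper limit of normal, whatever the cause. But Table 3 is organised by grade. Its grade 2 and grade 3 rows hold TH-302 for any toxicity outside short exception lists, and creatinine is in neither list. If the rise counts as grade 2 or 3 toxicity, TH-302 is held as well and the both-drugs bullet applies. The documents do not give the creatinine grading, so this cannot be settled from them.

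One candidate row remains, therefore, and it is uncertain. A sunitinib-only hold could also arise outside the tables, since section 6.3 provides for one-drug holds and section 6.3.3 leaves room for the investigator's judgement.

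**Step 5: size of the difference at one visit.** There are two infusions per cycle (section 6.1.2). At the starting dose, 2 × 340 = 680 mg/m² per cycle, and one infusion is 340 / 680 = 50%. At the reduced level, 2 × 280 = 560 mg/m², and 280 / 560 = 50%. This is what turns on the choice of rule at one affected visit. It is not an expected loss of exposure across the trial.

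**The case against.** The strongest defence is that the two rules address different things. Section 6.3 concerns a single skipped dose at one visit. The ban stands under a heading on discontinuation, between a sentence on patients who stop TH-302 and one on patients who permanently stop both drugs. It can be added that the ban is express and specific to TH-302 while the bullet is generic, so a site that reads both has grounds to let the ban govern. Both readings are possible, but neither is stated. Step 2 shows that the wording does not hold the line between postponing and discontinuing, and the two readings lead to different actions at the same visit.

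Some of the defence stands in full. Section 6.3 never names TH-302 in this bullet, so the direction to give it alone follows from applying a general rule to one case. A reader might infer from the creatinine row that the tables themselves guarantee the conflict. They do not, because Table 3's grade rows may hold TH-302 for the same event. The SAP also reports part of what is needed: Tables 9 and 11 give omissions and reasons for each drug, and Table 14 lists patients who missed sunitinib or TH-302 in a cycle. None of these is designed to identify an individual infusion given during a sunitinib hold.

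**Conclusion.** The contradiction is real and confined to one situation: only sunitinib is held on day 8 or 22. It rests on the literal wording of section 6.3 and on the absence of any text limiting the ban in section 6.3.1. At an affected visit, half of the cycle's planned TH-302 depends on which section the site follows.

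Three stronger conclusions might be drawn, and the documents support none of them. First, that patients are in fact treated differently between sites: this is a foreseeable consequence, but no such event is reported. Second, that every infusion is affected because the bullet covers both infusion days: that describes the rule's reach, and no frequency of sunitinib-only holds is given. Third, that the efficacy decision is compromised: the two-stage design figures (18 and 43 patients, at least 3 and at least 8 responses) do not depend on this point. What remains is an internal inconsistency in a dosing instruction. It bears on patient safety and on the record of TH-302 exposure, and it is cheap to remove.

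**What to change.** Reconcile sections 6.3 and 6.3.1 so that a single order applies on day 8 or 22 when only sunitinib is held. Split the section 6.3 bullet in two, one for TH-302 held and one for sunitinib held, so that it no longer reads the same way in both directions. Which order applies is for the sponsor to decide; this review takes no position on it.

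In the SAP exposure section, add a listing that flags every TH-302 infusion given while sunitinib was held, by patient and cycle.

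The cost is a wording amendment, a notice to sites and one extra listing. No additional patients or procedures are needed.
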